Preliminary clinical data suggest that restoration of the GH axis in obesity is a potential therapeutic strategy in NAFLD. Our group demonstrated that once daily GH administration by subcutaneous injection with an increase in IGF-1 levels to the upper-normal range reduced IHL by 1H-MRS in overweight/obese individuals unselected for NAFLD.[29] Of importance, only a subset of study subjects would have qualified as having NAFLD. Despite this, we detected a decrease in IHL. These pilot data are exciting with regard to the potential for GH augmentation as an effective therapeutic strategy in NAFLD. **However, studies demonstrate that GH pulsatility may be particularly important for effective lipolysis,[43] and that a more continuous (versus pulsatile) administration of GH may downregulate GH signaling pathways.[44]** Thus importantly, in contrast to once daily GH administration, restoration of endogenous GH pulsatility via a GH secretagogue like ibutamoren may enhance the lipolytic effects of GH[43, 44] while preserving endogenous feedback loops, enhancing both efficacy and safety profiles.

A6. SCIENTIFIC PREMISE AND HYPOTHESIS:

The proposed intervention, ibutamoren, is an orally administered, long-acting ghrelin mimetic that has direct immune effects that target specific areas of known immune dysregulation in NAFLD/NASH, physiologically restores endogenous GH pulse amplitude, and has a strong safety profile with prior administration in over 1,200 individuals (adults and children).[45-53] **Our overarching hypothesis is that oral ibutamoren administration will improve steatosis, inflammation and fibrosis in subjects with overweight/obesity and NASH.**

2. Specific Aims and Objectives

A. SPECIFIC AIM 1: We hypothesize that GH augmentation by oral ibutamoren for 6 months in subjects NAFLD compared to an historically studied placebo group subjects for 6 months will:

Aim 1A: Decrease hepatic steatosis, as measured by 1H-MRS (**primary endpoint**)

Aim 1B: Decrease hepatic inflammation and fibrosis, as measured by
[REDACTED] (**primary endpoint**)

3. General Description of Study Design

[figure not shown]
Overview of Study Design (Figure 1, Table 1)

An overview of the study design is provided in Figure 1. Aim 1 examines the effect of Ibutamoren mesylate administration on intrahepatic lipid accumulation in 10 men and women with NAFLD and relative IGF-1 deficiency.

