This study also investigates potential mediators of GH-induced decrease in intrahepatic lipid accumulation, including insulin/glucose and lipids, as well as body composition parameters. Ibutamoren will be dosed at 25 mg daily after completion of all baseline tests.

Figure 1 Study Design: 6-month, open-label administration of ibutamoren mesylate 25 mg daily in subjects with NAFLD.

Aim 1A investigates the 6-month change in intrahepatic lipid content by ¹H-MRS (*primary endpoint*) and **AIM 1B** investigates the 6-month change in hepatic inflammation and fibrosis [REDACTED] (*primary endpoint*) with GH augmentation by ibutamoren versus historical placebo-treated controls studied under identical procedures. Additional endpoints include change in NAFLD Fibrosis score and body composition by DXA.

Participants from the Protocol [REDACTED] will be used to formulate a control group for analysis.

4. Subject Selection

III. SUBJECT SELECTION

A. Inclusion/Exclusion Criteria

- **Aim 1:** Subjects: N=15 (goal of 10 completers) with NAFLD/NASH.
 - **Inclusion Criteria:**
 - Age 21-60yo and generally healthy
 - $BMI \geq 25 \text{ kg/m}^2$
 - $BMI \geq 23 \text{ kg/m}^2$ for subjects whose background is South Asian, Chinese, Middle Eastern, Black African, or African-Caribbean.

- Radiographic or histologic diagnosis of NAFLD / NASH
- IGF-1 level <3rd quartile of normal for age.

○ **Exclusion Criteria:**

1. Contraindications to MRI imaging (primary endpoint)
2. Diabetes mellitus, defined as fasting glucose ≥ 126 mg/dL or hemoglobin A1C ≥ 6.5 or use of any medications prescribed to treat hyperglycemia is exclusionary for Aim 1.
 - a. Subjects whose fasting glucose result at the screen visit is ≥ 126 mg/dL and who do not have a prior history of diabetes mellitus will be offered an optional retest with inclusion if subsequent repeat fasting glucose is < 126 mg/dL. Subjects with repeat glucose ≥ 126 mg/dL will be excluded from the study.
3. History of cancer/malignancy of any organ system other than previously fully resected basal cell carcinoma of the skin
4. Significant renal disease.
5. Unwilling or unable to perform age- and sex-appropriate cancer screening such as mammogram, PAP and/or colonoscopy
6. Decompensated or unstable cardiovascular disease (for example, heart failure, unstable coronary disease, uncontrolled arrhythmias) at the discretion of the study physician
7. Active carpal tunnel syndrome

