6. STUDY PROCEDURES

Table 1. Aim 1 Schedule of Procedures

Open label ibutamoren mesylate (oral 25 mg daily) will be administered to 12 subjects (goal 10 completers) with comparison to identically-studied, historical placebo-group controls.

Visit Components	Screen	Baseline	1 month	2 month lab check	3 month	4.5 lab check	6 month
COVID-19 Screening Phone Call	x	x	x	x	x	x	x
Liver Ultrasound	x						
NAFLD Fibrosis Score		x					x
DXA		x					x
MRI/MRS		x					x
Waist-Hip Ratio		x					x
Endocrine/Misc. Labs							
Blood: TSH	x						
Blood: HCV Antibody	x						
Blood: HBV Surface AG	x						
Peripheral Blood Mononuclear Cells (PBMCs)		x					x
Ibutamoren Stimulation Test		x					
Blood: Insulin, lipids		x					x
Safety Evaluation							
Physical Exam***	x	x	x		x		x
Blood: INR	x						
Blood: Creatinine	x						
Blood: CBC	x						x
Blood: Liver function tests	x	x	x	x	x	x	x
Blood: Fasting Glucose	x	x	x		x		x
Blood: HbA1c	x				x		x
Blood: IGF-1	x		x		x		x
Urine pregnancy test	x	x	x		x		x

*** Optional, limited physical exam will be performed at the discretion of the study provider

A. Study Visits for Specific Aim 1:

1. Screening Visit : (n=50, approximately 50% women)

After informed consent, subjects will be evaluated for eligibility with:

- A basic metabolic panel, INR, CBC, TSH, fasting glucose, hemoglobin A1c (HbA1c), hepatic function panel, and IGF-1 will be performed.
- Records of cancer screenings appropriate for the age and gender of the participant will also be requested.
- Height and weight will be measured, and BMI will be calculated.
- A history and physical will be performed.
- A pregnancy test will be performed in all premenopausal women with childbearing potential.
- A liver US or liver ultrasound elastography [REDACTED] will be performed in study subjects who do not have a known diagnosis of NAFLD.
 - Due to limited ultrasound sensitivity for screening for fatty liver, subjects will be invited to a screening MRI for assessment of NAFLD if the subject otherwise qualifies for the study but has a negative screen ultrasound for NAFLD.
- Individuals will be queried regarding alcohol use as well as for history of other chronic liver disease.
- Hepatitis C antibody and Hepatitis B surface antigen tests will be performed in study subjects who have not had this as a part of their clinical care.
- Serum and plasma samples will be drawn and stored frozen for future testing.

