Remote Blood Draws for Screening [REDACTED]: to allow maximum flexibility with our subject's schedules, the blood tests listed above can be drawn at [REDACTED] facility close to the subject's home location. Screen aliquots will not be obtained during a remote blood draw.

2. Baseline and 6-month visit: (n=15 at baseline, n=10 completers: approximately 50% women)

The baseline visit will occur within 12 weeks after the screening visit. The following assessments will be made during the baseline visit, which will occur within a 30-day period and can occur in one session or over multiple days depending on schedules and patient preference. The 6-month visit will be performed during a +/- 3 week interval around the indicated return time to allow for potential scheduling conflicts. The order of the tests may vary depending on the subject and TCRC availability.

- Interview to determine whether any changes in medical history since the screening visit has occurred
- BMI, waist-hip-ratio measured
- In the fasting state, a blood sample will be obtained to determine glucose, insulin, GH, IGF-1 (6 mo only), CBC (6 mo only), HbA1c (6 mo only), lipids, triglycerides, and liver function tests. Note: Pre-treatment HbA1c, IGF-1, CBC will have already been performed at the screening visit and are not repeated at baseline.
- Fasting glucose will be performed at baseline and 6-month visits. Aliquots for insulin measurements will be taken at these time points as well.
- A fasting GH-stimulation test will be performed at the baseline visit only using ibutamoren 25 mg oral dose with GH levels measured at 0, 30, 60, and 90 and

120 minutes. All hormones will be measured using gold standard techniques (including IGF-1 by LC/MS).

- Serum and plasma samples will be drawn and stored frozen for future testing.
- [REDACTED]
- MRI: 1H-MRS of the right hepatic lobe will be performed at the baseline and 6-month visits to quantify hepatic lipid content and other fat depots. [REDACTED] sequences will also be performed for noninvasive analysis of hepatic iron content, inflammation and fibrosis. Sequences will also be performed to assess pancreatic fat, inflammation and fibrosis as well as renal inflammation and fibrosis. The entire protocol will be scheduled for one 45 minute MRI slot.
 - A baseline MRI will be acquired if the screen MRI occurred more than 6 weeks prior to baseline procedures. Otherwise, the MRI procedure at baseline is not required.

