Dosing for Aim 1: Ibutamoren mesylate will be dosed at 25 mg daily. Dosing may be reduced to 18 mg daily for an IGF-1 level above the normal range or GH-related side effects, but this is not expected based on prior studies of ibutamoren. Ibutamoren can be taken with or without food.

1 Month Post-Study Follow Up Call:

A study provider will attempt to contact subjects four weeks after study completion to document subject status at that time, which will be approximately one month after study drug discontinuation. Any remaining study results will be reviewed with the subject at that time.

REMOTE CONSENT AND VISIT PROCEDURES:

REMOTE CONSENT AND SCREEN MEDICAL HISTORY:

In order to minimize potential COVID-19 exposures for study staff and subjects, consent and partial screening procedures may be performed virtually (via phone or MGB approved video platform) prior to an in-person portion of the visit. We will follow all MGB eConsent procedures. After consent via an MGB approved e-consent platform (via REDCap), the study provider will perform the screen medical history. The subject will also be instructed on how to fill out screen-related forms electronically. The subject will be told immediately via phone if the provider determines by history alone that they would be ineligible for the study. If the subject otherwise appears to be eligible based on history, they will be invited for an in-person portion of the screen visit that includes the limited physical exam, vital signs, blood draw and ultrasound or liver ultrasound elastography [REDACTED] as needed for diagnosis of NAFLD. [REDACTED]

A high-contrast, black and white image showing a series of horizontal bars of varying lengths and positions. The bars are set against a white background and appear to be composed of multiple horizontal segments, suggesting a digital or processed signal. The bars are located in the upper half of the frame, with some extending towards the bottom edge.

Payment for Study Procedures

We will provide parking at MGH garages free of charge and will additionally reimburse [REDACTED] for travel to/from MGH for each visit.

ADDITIONAL REIMBURSEMENT: Subjects will be reimbursed [REDACTED] each additional blood draw related to glucose monitoring procedures or study discontinuation.

Communication Via Text Messages (SMS)

Following MGB policy regarding text messages, if subjects agreed to be contacted via text

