Human Subjects Involvement and Characteristics: This study will enroll a total of 50 (50 for Aim 1, and 10 Aim 1 participants for Aim 2) obese, otherwise healthy, individuals ages 21 to 60 (approximately 50% women). Subjects must be healthy, with no history of cardiovascular disease, renal impairment, diabetes or malignancy. Rationale for exclusions is discussed in the study protocol; in brief, these exclusions are designed to 1) exclude men and women at greatest risk for significant adverse events and 2) avoid confounding effects of medical conditions and medications. We exclude children and young adults through age 20 because GH administration in children prior to growth plate fusion causes linear growth, and GH administration could cause an increase in height.

Dose Rationale: The ibutamoren mesylate 25 mg oral daily dosing was selected due to evidence for both effective augmentation and safety in the adult target population. The proposed dose of 25 mg oral ibutamoren daily effectively augments IGF-1 levels by approximately 40-84%, which is within the range of normal.^{53, 56} Fixed dose ibutamoren mesylate at 25 mg daily has been shown to augment IGF-1 levels by 40% in healthy obese men⁵⁶, which is comparable to or slightly below the 50% increase in IGF-1 levels we achieved (targeting upper-normal IGF-1 levels) with daily, subcutaneous GH administration at 6 weeks in a similar population.²⁹ Additionally, this is within the range of IGF-1 augmentation seen in patients with HIV-associated

NAFLD with the subcutaneously administered GHRH analogue tesamorelin, which augmented IGF-1 by approximately 59% with a net treatment effect of a 2.9% decrease in liver fat.⁵⁷ There is additional direct evidence with ibutamoren that this GH augmentation leads to effective GH-related augmentation of metabolism and body composition. This includes studies of the 25 mg dose of ibutamoren mesylate that have demonstrated an increase in fat free mass in healthy, older adults (ages 60-81 years) at 12 months⁴⁶ and a transient increase in basal metabolic rate and an increase in fat free mass in healthy adults with obesity at 2 months.⁵⁶ These investigations are promising regarding safe and effective GH-augmentation by 25 mg daily ibutamoren mesylate and impacts on fat-free mass, and we now propose to study the impact of this dose of ibutamoren on hepatic steatosis, inflammation and fibrosis, endpoints which were not assessed in prior trials of ibutamoren mesylate at this dose.

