[REDACTED] we will have 80% power to detect a 2% absolute difference in change in liver fat between GH and placebo utilizing an estimated SD of the change in liver fat of 1.6% based on a study of a diet-based intervention for NAFLD.[65] Notably, this calculation already allows for a generous dropout rate of 17% (2 dropouts from 12 enrolled). Additionally, Stanley *et al.*[66] reported a 2.9% change between a subcutaneous GH secretagogue and placebo, which is likely an underestimation of our expected effect given that study involved subjects unselected for NAFLD.

Aim 1B Statistical Power: The primary endpoint is the cT₁ Score by [REDACTED] We will have 80% power for a cohort of N=20 subjects with a two-tailed significance level of 0.05 to detect a difference of 76 ms in cT₁ between the ibutamoren and placebo groups assuming a SD of 57.4 ms as reported in a NAFLD treatment-study by Harrison *et al.*[67] Allowing for dropouts (n=18), the detectable difference in cT₁ is 80 ms. [REDACTED]

Aim 1A and 1B Data Analysis Plan: A pooled random slopes model analysis of treatment effect across sexes with weights equaling the frequency of sexes in the sample. A secondary analysis will test for the treatment-sex interaction. For all analyses, an intent-to-treat analysis will be performed. We will apply guidelines developed by the National Research Council regarding missing data.⁶⁶ Our primary analysis assumes that data is missing at random. We will conduct two sensitivity analyses: (1) assumes that the missing data is a function of the unobserved random effect⁸² and (2) tests the model's assumptions under other missingness mechanisms.⁸³

[REDACTED]

[REDACTED]

[REDACTED]

10. Monitoring and Quality Assurance

A number of procedures will be instituted to protect against potential risk involved in this prospective protocol, as follows:

[figure not shown]

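### An undated NAFLD diagnosis waives screening imaging and no pre-drug MRS result governs entry, so the treated effect can be diluted, and entry does not support a conclusion about NASH

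*Combined protocol and SAP*

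**What the plan says.** **Entry.** The liver criterion in Section 4 is "Radiographic or histologic diagnosis of NAFLD / NASH". It gives no date limit and no minimum liver fat, cT1, stiffness or fibrosis score. The severity limits among the exclusions (transaminases above 300 U/L, cirrhosis, hepatic impairment) are all upper limits.

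**Screening imaging.** Under the Screening Visit in Section 6, liver ultrasound or elastography "will be performed in study subjects who do not have a known diagnosis of NAFLD". The remote-visit text in the same section says it is done "as needed for diagnosis of NAFLD". MRI at screening is a second step after a negative ultrasound: "subjects will be invited to a screening MRI for assessment of NAFLD if the subject otherwise qualifies for the study".

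**Pre-drug MRI/MRS.** Section 6 schedules MRS at baseline and 6 months. A recent screening scan may stand in for the baseline one: "A baseline MRI will be acquired if the screen MRI occurred more than 6 weeks prior to baseline procedures". Drug starts once baseline procedures are complete. No MRS or cT1 value is made a condition for starting.

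**Hypothesis.** Section 1 (A6) expects that ibutamoren "will improve steatosis, inflammation and fibrosis in subjects with overweight/obesity and NASH". Aim 1 in Section 2 and the enrolment text in Section 5 refer to NAFLD.

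**Expected effect.** Section 9 calls the 2.9% liver-fat effect of an earlier study "likely an underestimation of our expected effect given that study involved subjects unselected for NAFLD". The Dose Rationale in Section 7 places a 2.9% effect in patients with HIV-associated "NAFLD with the subcutaneously administered GHRH analogue tesamorelin, which augmented IGF-1 by approximately 59" percent.

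**The concern.** Both primary endpoints are falls from baseline. A fall of 2 percentage points of liver fat needs liver fat to lose, and a fall of 76 ms in cT1 needs a raised cT1. The entry rules establish that a subject was once diagnosed, not that disease is present now. The named recruitment sources include fatty liver and GI clinics and a NAFLD cohort, so some subjects will arrive already diagnosed and skip the scan.

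A further safeguard is loose. Section 7 lists unstable weight before entry as an exclusion, but it is not among the 18 numbered exclusions in Section 4 and has no threshold or window. Fat lost with weight since diagnosis is therefore not clearly screened out.

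Section 9 itself treats effect size as depending on selection for NAFLD. With 10 treated completers, one or two subjects with nothing to lose would shift the mean noticeably.

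The NASH wording is a second mismatch. No sign of inflammation or fibrosis is required at entry, so the treated group cannot be presumed to have NASH.

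**Working it through.** **Inputs (Section 9).** 10 treated and 10 historical controls. Aim 1A: difference 2 points, SD of change 1.6. Aim 1B: difference 76 ms, SD 57.4. Two-sided alpha 0.05 is stated for Aim 1B and assumed here for Aim 1A, which states none.

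**Step 1: the plan's own power.** Standardised shift = d / (SD × √(2/n)).
- Aim 1A: 2 / (1.6 × √0.2) = 2.795. Normal approximation: Φ(2.795 − 1.960) = 79.8%, which reproduces the stated 80%. The two-sample t-test (18 df, critical value 2.101) gives 75.3%.
- Aim 1B: 76 / (57.4 × √0.2) = 2.961. The t-test gives 79.9%, which reproduces the stated 80%.

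The t-test is used for both aims below, so Aim 1A starts from 75%. The gap between 75% and 80% comes from the formula and is not part of this point.

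**Step 2: dilution.** Assumption, not in the documents: k of the 10 treated completers have mean change 0 and the others show the full planned effect. The mean effect becomes d × (1 − k/10). Mixing two means also widens the spread in the treated arm, so power was simulated (400,000 trials per cell, pooled t-test).

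The SD of change in non-responders is also unknown. A subject with almost no liver fat should vary less than 1.6 points, so three values were tried: the planning SD, half of it, and 0.5/1.6 of it.

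| k | Aim 1A mean effect | Power, non-responder SD 1.6 / 0.8 / 0.5 | Aim 1B mean effect | Power, non-responder SD 57.4 / 28.7 / 17.9 |
|---|---|---|---|---|
| 0 | 2.0 points | 75% | 76 ms | 80% |
| 1 | 1.8 | 63 / 65 / 66% | 68.4 | 68 / 70 / 71% |
| 2 | 1.6 | 51 / 54 / 55% | 60.8 | 55 / 59 / 60% |
| 3 | 1.4 | 39 / 42 / 43% | 53.2 | 42 / 46 / 47% |

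Shifting the mean alone and leaving the SD unchanged gives slightly higher figures: 66, 56 and 46% for Aim 1A, and 71, 61 and 50% for Aim 1B.

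**Step 3: NASH.** The hypothesis names NASH. Inclusion accepts NAFLD or NASH, enrolment describes NAFLD, and the title of the trial that supplies the cT1 SD (reference 67) names patients with nonalcoholic steatohepatitis. Nothing at entry separates NASH from simple steatosis, and 10 completers leave no usable NASH subgroup.

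**Step 4: the 2.9% study.** Section 9 cites reference 66, whose title describes HIV-infected patients with abdominal fat accumulation. That fits a sample not selected for NAFLD. The Dose Rationale gives the same 2.9% for tesamorelin but describes HIV-associated NAFLD and cites number 57, which in the reference list is an MR spectroscopy paper. The Dose Rationale is the text to check first.

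**The case against.** **A null result is not uninterpretable.** A reader might infer that a null result could not tell an ineffective drug from absent disease. The documents do not support that. Every treated subject has MRS and the inflammation and fibrosis sequences before drug, so low baseline values would be seen. This objection stands and limits the harm to dilution.

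**Table 1 does not promise an ultrasound for everyone.** Its screening ultrasound row carries an unqualified mark, which might be read as a scan for all. But the table marks other conditional tests in the same way: the hepatitis B and C tests, which the text limits to subjects not already tested, and the 2-month liver panel, which depends on the 1-month result. The visit text governs, so added ultrasounds are a real, if small, cost.

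**The number affected is unknown.** It is tempting to say that most subjects would enter on an old diagnosis. The documents give neither the proportion already diagnosed nor the age of those diagnoses. Prior participants are described by overweight or obesity rather than NAFLD, advertisements are also used, and part of the recruitment text is redacted. That an old diagnosis is allowed is itself inferred from silence.

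**Some protection exists.** Pioglitazone and vitamin E are excluded, and the investigator may decline an unsuitable subject. Neither sets a requirement for current liver fat, so the gap remains.

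**Conclusion.** The point holds as a gap in entry confirmation and a mismatch in the population named. As written, the plan can admit a subject with no current steatosis and count that subject in both primary analyses. Under the stated assumption, one such subject among 10 costs about 9 to 12 percentage points of power on either endpoint, and two cost about 20 to 25. These figures illustrate sensitivity. They do not forecast what will happen, because neither k nor the variability of non-responders is in the documents.

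A reader might conclude that the trial cannot answer its question. That goes too far: Aim 1 is written for NAFLD and can be tested there. What entry does not support is a conclusion about NASH.

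Nor does the conflict over the 2.9% study mean that the argument in Section 9 must go. That argument agrees with the title of its cited reference. The conflict is minor and needs reconciling.

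**What to change.** 1. **Confirm current steatosis before drug start.** Either send subjects with an older known diagnosis through the existing ultrasound-then-MRI screening pathway, with a stated age beyond which a diagnosis no longer suffices, or give the already scheduled pre-drug MRS an entry role. The second uses the endpoint measurement itself and avoids the limited ultrasound sensitivity that Section 6 acknowledges, but the MRS must be read before treatment begins. The investigators should set the cut-off. Select the historical controls on their baseline MRS by the same rule, so that regression to the mean after selection affects both groups alike. Cost: some added ultrasounds under the first option, and a few more screen failures under either.
2. **Word the hypothesis and the Aim 1B conclusion as steatosis and cT1 in NAFLD**, unless evidence of NASH is made an entry requirement. Confirming steatosis does not guarantee a raised cT1, so this is needed even if item 1 is adopted. Cost: wording only.
3. **Reconcile the two descriptions of the 2.9% study** and check the citation number in the Dose Rationale. Cost: wording only.

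In the same edit, align the weight-instability exclusion in Section 7 with the numbered list in Section 4.
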